8.3.2 Unanticipated Problem Reporting

Incidents or events that meet the OHRP criteria for UPs require the creation and completion of an UP report form. It is the site investigator's responsibility to report UPs to their IRB. The UP report will include the following information:

- Protocol identifying information: protocol title and number, PI's name, and the IRB project number;
- A detailed description of the event, incident, experience, or outcome;
- An explanation of the basis for determining that the event, incident, experience, or outcome represents an UP;
- A description of any changes to the protocol or other corrective actions that have been taken or are proposed in response to the UP.

To satisfy the requirement for prompt reporting, UPs will be reported using the following timeline:

- UPs that are SAEs will be reported to the IRB within 3 days of the investigator becoming aware of the event.
- Any other UP will be reported to the IRB within 3 days of the investigator becoming aware of the problem.
- All UPs should be reported to appropriate institutional officials (as required by an institution's written reporting procedures) within 3 days of the IR's receipt of the report of the problem from the investigator.

8.3.3 Reporting of Pregnancy

Pre-menopausal persons of child-bearing age will be screened with a pregnancy test prior to enrollment. Pregnant people will be excluded from enrollment in this study. However, if an enrolled participant becomes pregnant after BCI is performed, they will be eligible to remain in the study without any modifications to study procedures.

8.4 Study Halting Rules

If 2 or more participants experience DLT at any dose level, then the prior dose will be determined to be the MTD and the study will be terminated. Participants already enrolled in the study will be followed post procedure as per protocol. The study will be terminated in the event of death, massive hemoptysis, or acute respiratory distress syndrome (ARDS).

Additionally, the study will be suspended when three grade 3 AEs determined to be "probably related.". The medical monitor will notify the investigators immediately when the third grade 3 event is reported and enrollment screens will stop accepting new study participants. The investigators will inform the DSMB members within 24 hours of this occurrence and will provide the DSMB with AE listing reports. The DSMB will convene an ad hoc meeting by teleconference or in writing as soon as possible. The DSMB will provide recommendations for proceeding or halting the study.

8.5 Safety Oversight:

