4.2 Study Endpoints

4.2.1 Primary Study Endpoints: Feasibility and Safety

- Each patient will be classified as having successfully undergone BCI or not. Feasibility of BCI is defined as successfully performing BCI in at least 80% of patients in whom BCI is attempted. Successful performance of BCI will require identification of the target peripheral lung tumor by radial endobronchial ultrasound within 20 minutes followed by completed cryoablation of target tumor. The target tumor will have freeze-thaw cycles applied every one centimeter of the largest diameter. Additional BCI features will be described as follows:
 - a) Ability of radial endobronchial ultrasound to identify peripheral lung tumor
 - b) Length of time to perform BCI
 - c) Length of time of fluoroscopy exposure during BCI
- 2) Dose-limiting toxicities (DLT) will be used to guide the dose-escalation procedure and determine the maximum tolerated dose. A DLT is defined as any of the following occurring up to 7 days post-BCI:
 - Grade 2 or 3 bleeding, based on the following scale (34):
 - a) Grade 0: absence of bleeding
 - b) Grade 1: bleeding requiring suctioning to clear
 - c) Grade 2: bleeding requiring an endoscopic procedure (iced saline, 1:20,000 topical epinephrine, or bronchial occlusion)
 - d) Grade 3: severe bleeding (>100cc total volume). Severe bleeding will also be defined as bleeding which cannot be controlled endoscopically, requires ICU admission or interventional radiology/ surgical intervention, or results in respiratory or hemodynamic instability (34)
 - Pneumothorax necessitating tube thoracostomy; recorded features of pneumothorax to include:
 - a) size
 - b) associated symptomatology
 - c) respiratory impairment
 - d) need for chest tube placement
 - Any NCI CTCAE (33) grade 3, 4, or 5 adverse events, which may be possibly, probably, or definitely related to BCI

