5.8 Premature Termination or Suspension of Study

This study may be temporarily suspended or prematurely terminated if there is sufficient reasonable cause. Written notification, documenting the reason for study suspension or termination, will be provided by the suspending or terminating party regulatory authorities. If the study is prematurely terminated or suspended, the PI will promptly inform the IRB and will provide the reason(s) for the termination or suspension.

Circumstances that may warrant termination or suspension include, but are not limited to:

- Determination of unexpected, significant, or unacceptable risk to participants
- Demonstration of efficacy that would warrant stopping
- Insufficient compliance with protocol requirements
- Data that are not sufficiently complete and/or evaluable
- Determination of futility

Study may resume once concerns about safety, protocol compliance, data quality are addressed and satisfy the IRB.

6 Procedural Intervention

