6.1.2 Dose Escalation Protocol

A standard 3+3 dose escalation strategy will be used. The table below shows the doses that will be provided. Three participants will be initially enrolled at Level 1. If none of the first three participants at a given dose experiences dose-limiting toxicity (DLT), the dose will be escalated. If two or more of the first three participants experience DLT, the prior dose will be deemed the maximum tolerated dose (MTD) and the study will be terminated. If one of the first three participants experiences DLT, an additional three participants will be enrolled at the same dose. If among these six, only one experiences DLT, the dose will be terminated. If two or more of six experience DLT, the prior dose will be deemed the MTD and the study will be terminated. If the MTD is reached and only three participants have been treated at that dose, an additional three will be treated to ensure six subjects are treated at the MTD. DLT are defined in Section 4.1.1 (Primary Study Endpoints: Feasibility and Safety).

| Dose Level | Freeze Time (per site) | Thaw Time |
|------------|------------------------|---|
| Level 1 | 1 second | Will last until the probe separates from target tissue* |
| Level 2 | 2 seconds | Will last until the probe separates from target tissue* |
| Level 3 | 3 seconds | Will last until the probe separates from target tissue* |
| Level 4 | 5 seconds | Will last until the probe separates from target tissue* |
| Level 5 | 10 seconds | Will last until the probe separates from target tissue* |
| Level 6 | 20 seconds | Will last until the probe separates from target tissue* |

CONFIDENTIAL

| Level 7 | 30 seconds | Will last until the probe separates from target |
|---------|------------|---|
| | | tissue* |

6.1.3 **Procedures for Training of Clinicians on Procedural Intervention**

The NYU Interventional Pulmonary service has extensive experience using the flexible cryoprobe for debulking of central airway tumors. BCI will be performed by a board-certified, NYU Interventional Pulmonologist.

Only patients with the presence of a bronchus or airway path leading directly to the peripheral lung tumor will be eligible to undergo BCI. The peripheral tumor will also need to be identified by radial EBUS prior to performing BCI. If the peripheral tumor is unable to be identified by radial ultrasound within 20 minutes, then the patient will not be a candidate to undergo BCI.

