8.1 Specification of Safety Parameters

Dose-limiting toxicities (DLT) will be used to guide the dose-escalation procedure and determine the maximum tolerated dose. A DLT is defined as any of the following occurring up to 7 days post-BCI:

- Grade 2 or 3 bleeding, based on the following scale (34):
 - a) Grade 0: absence of bleeding
 - b) Grade 1: bleeding requiring suctioning to clear
 - c) Grade 2: bleeding requiring an endoscopic procedure (iced saline, 1:20,000 topical epinephrine, or bronchial occlusion)
 - d) Grade 3: severe bleeding (>100cc total volume). Severe bleeding will also be defined as bleeding which cannot be controlled endoscopically, requires ICU admission or interventional radiology/ surgical intervention, or results in respiratory or hemodynamic instability (34)
- pneumothorax necessitating tube thoracostomy; recorded features of pneumothorax to include:
 - a) size
 - b) associated symptomatology
 - c) respiratory impairment
 - d) need for chest tube placement
- any NCI CTCAE (33) Grade 3, 4, or 5 adverse events, which may be possibly, probably, or definitely related to BCI

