8.2.2 Relationship to BCI

The clinician's assessment of an AE's relationship to BCI is part of the documentation process, but it is not a factor in determining what is or is not reported in the study. If there is any doubt as to whether a clinical observation is an AE, the event should be reported. All AEs must have their relationship to study agent assessed. In a clinical trial, the study product must always be suspect. To help assess, the following guidelines are used.

- **Related** The AE is known to occur with cryoablation, there is a reasonable possibility that the study agent caused the AE, or there is a temporal relationship between the study agent and event. Reasonable possibility means that there is evidence to suggest a causal relationship between the study agent and the AE.
- Not Related There is not a reasonable possibility that BCI caused the event, there is no temporal relationship between the study agent and event onset, or an alternate etiology has been established.

For all collected AEs, the clinician who examines and evaluates the participant will determine the AE's causality based on temporal relationship and his/her clinical judgment. The degree of certainty about causality will be graded using the categories below.

- **Definitely Related** There is clear evidence to suggest a causal relationship, and other possible contributing factors can be ruled out. The clinical event, including an abnormal laboratory test result, occurs in a plausible time relationship to drug administration and cannot be explained by concurrent disease or other drugs or chemicals. The response to withdrawal of the drug (dechallenge) should be clinically plausible. The event must be pharmacologically or phenomenologically definitive, with use of a satisfactory rechallenge procedure if necessary.
- **Probably Related** There is evidence to suggest a causal relationship, and the influence of other factors is unlikely. The clinical event, including an abnormal laboratory test result, occurs within a reasonable time after BCI, is unlikely to be attributed to concurrent disease or other drugs or chemicals.

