8.3 Reporting Procedures

8.3.1 Adverse Event Reporting

Any adverse events or serious adverse events possibly, probably, or definitely related to BCI will be reported in real-time notification by the clinical investigators to the Data and Safety Monitoring Board and Data Coordinating Center. In accordance with 21 CFR 812.150(a)(1), the clinical investigators will also report to the IRB as soon as possible and within 10 working days.

In the event of any unexpected fatal or life-threatening suspected adverse reaction, the Data and Safety Monitoring Board and IRB will be notified as soon as possible and within 2 working days.

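### The three-event suspension rule in section 8.4 literally leaves out definitely related and grade 4 events, and its next sentence uses a different trigger: probably a drafting omission with a small effect, but worth correcting

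*Combined protocol and SAP*

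**What the plan says.** Section 8.4 (Study Halting Rules) has three layers. Two or more participants with a dose-limiting toxicity (DLT) at one dose level end the study. A death, massive hemoptysis or ARDS also ends it. In addition, "the study will be suspended when three grade 3 AEs determined to be" probably related. That sentence is visibly incomplete: it has no verb after the event count, and nothing says that the attribution is a minimum. The next sentence has the medical monitor alert the investigators "when the third grade 3 event is reported and enrollment screens will stop accepting new study participants". The DSMB must then be told within 24 hours and hold an ad hoc review.

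Section 8.2.2 grades causality on a scale where definitely related sits above probably related and has its own definition: "There is clear evidence to suggest a causal relationship, and other possible contributing factors can be ruled out".

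Where the protocol means several attribution levels, it lists them. The DLT definition in 4.2.1 includes "Any NCI CTCAE (33) grade 3, 4, or 5 adverse events, which may be possibly, probably, or definitely related to BCI". Section 8.1 repeats it ("adverse events, which may be possibly, probably, or definitely related to BCI"), and 3.1 and 8.3.1 name the same three levels. Section 8.5.1 refers back to 8.4 for the stopping rules and does not restate them.

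**The concern.** Taken at its word, the first sentence gives no weight to a grade 3 event judged definitely related, nor to a grade 4 event of any attribution. The second sentence goes the other way and would count even an unrelated grade 3 event. A predefined halting rule in a first-in-human study should give one count.

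What is at stake is limited: the automatic enrollment stop, the 24-hour DSMB notice and the ad hoc meeting. These matter for related events that the DLT rule does not add together, namely one per dose level, or starting after the 7-day DLT window. Section 8.2.4 has AEs recorded well beyond day 7, so such late events would be on file.

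**Working it through.** **1. The two sentences applied to the same events** (events spread so that the DLT rule is not met)

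| Events | Sentence one, literal | Sentence two, literal | Grade 3 or higher, probable or definite |
|---|---|---|---|
| Three grade 3, probable | met | met | met |
| Two grade 3 probable, one grade 3 definite | not met | met | met |
| Three grade 3, definite | not met | met | met |
| Two grade 3 probable, one non-fatal grade 4 probable | not met | not met | met |
| Three grade 3, unrelated | not met | met | not met |

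The sentences agree with each other in the first and fourth rows only, and in the fourth both miss the pattern.

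**2. Does another fixed rule catch scattered events?** Section 6.1.2 points to the 4.2.1 definition by title, under an old number ("DLT are defined in Section 4.1.1 (Primary Study Endpoints: Feasibility and Safety"). On that definition, a related grade 3 event within 7 days is a DLT. Whether one DLT in six lets the trial move on can be checked against the table in 10.5. With DLT rate p, escalating on 0 of 3 or 1 of 6 has probability (1 − p)³ + 3p(1 − p)² × (1 − p)³. At p = 0.10 this is 0.729 + 3 × 0.10 × 0.81 × 0.729 = 0.906, which matches the printed 0.91. So 1 of 6 escalates, in line with 10.4.3. One DLT in six at each of three levels (18 participants, 3 events) therefore passes the 3+3, and the count in 8.4 is the only fixed rule for that pattern.

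**3. Size of the omission of definite events.** The documents state no operating characteristic for this rule, so there is no figure to reproduce. Assumptions, none of them from the documents:
- every probably or definitely related grade 3 AE is a DLT;
- the rate q per participant is constant across levels (5%, 10% or 15%);
- a share s of these events is judged definite (10% in the main case).

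From the documents: seven levels (6.1.2), a cap of 24 (Protocol Summary), and the 3+3 rules as read in step 2.

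The calculation goes through participants one at a time. Each has no event (probability 1 − q), a counted event (q(1 − s) under sentence one) or an uncounted event (qs). The trial moves up after 0 of 3 or 1 of 6 and ends at the second DLT in a level; that terminating event is not counted. The result is the probability of three counted events while the trial is still open.

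| Rate q | Both categories count | Sentence one alone, s = 10% | Gap, s = 10% | Gap, s = 5% | Gap, s = 2% |
|---|---|---|---|---|---|
| 5% | 0.0274 | 0.0202 | 0.7 points | 0.4 | 0.2 |
| 10% | 0.0872 | 0.0648 | 2.2 points | 1.2 | 0.5 |
| 15% | 0.1142 | 0.0856 | 2.9 points | 1.5 | 0.6 |

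Hand check: given three such events, at least one is definite with probability 1 − 0.9³ = 0.271, so sentence one alone fails to trigger at the third event in 27% of cases. Multiplying, 0.0872 × 0.729 = 0.0636, slightly below 0.0648 because a later probable event can still complete the count.

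Two limits apply. The extra participants treated at the MTD under 6.1.2 are not modelled; they would raise both probabilities and the gap. The omission of grade 4 events is not sized, because the documents give nothing on the split by grade.

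**The case against.** The strongest reply is that nobody would apply the rule this way. The sentence is plainly unfinished. An event with clear evidence of causality satisfies the description of probably related with room to spare, so that term reads naturally as a floor. The reference to the third grade 3 event can be read as pointing back to the events just named. If it is read literally instead, it covers definite events. Either way, two probable events and one definite event lead to a stop. Much of this stands: for definite grade 3 events, harm requires the first sentence to be read literally and alone, and the gap is zero if the second sentence is followed as written. It does not remove the conflict between the sentences or supply the missing grade 4 events.

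Other safeguards also stand. Two participants with a DLT at one level end the study. Related AEs "will be reported in real-time notification by the clinical investigators to the Data and Safety Monitoring Board". The medical monitor reviews cumulative safety under 8.5.1, and 5.8 permits suspension on "Determination of unexpected, significant, or unacceptable risk to participants". None of these is a fixed count that pools non-catastrophic events across levels. Section 3.1 lists only grade 4 or 5 CTCAE events as DLTs. On that wording a grade 3 AE other than bleeding, or a pneumothorax needing a chest tube, would not be a DLT and would depend on 8.4 alone.

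A reader might infer that the gap is large. Treating all 24 participants with no 3+3 stopping, a 10% rate and half of events judged definite, the binomial chance of three counted events is 0.436 against 0.116. The documents do not support those inputs: the 3+3 would often stop first, and a definite judgment requires other causes to be ruled out. That is hard after a single BCI given in the same session as a standard-of-care bronchoscopy that may include biopsies.

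**Conclusion.** The rule is wrong as written. Its first sentence counts only probably related grade 3 events and so omits definitely related and grade 4 events; its second sentence uses another trigger; and no other section corrects this.

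It is most likely a drafting omission. A reader might infer that the sponsor chose to exclude definite events, or that such events would escape oversight. Neither follows: the protocol includes definite events wherever it lists attributions, and the DLT rule and real-time reporting cover most of them.

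The effect is small: about 1 to 3 percentage points at assumed rates of 5% to 15% and a 10% definite share, 0.2 to 0.6 points at a 2% share, and none for definite grade 3 events if the second sentence is followed literally. No estimate, test or MTD rule depends on it. It should be corrected because it is an operative halting rule and the correction is cheap.

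**What to change.** Amend both sentences in 8.4 so that they describe the same events:
- Sentence one: suspend once three AEs of grade 3 or higher have been judged probably or definitely related to BCI.
- Sentence two: the monitor's alert and the enrollment stop follow report of the third such event (grade 3 or higher, probably or definitely related to BCI).

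The words *or higher* are needed. Adding only *definitely* would still leave two related grade 3 events plus one related non-fatal grade 4 event short of the count. Leave immediate termination for death, massive hemoptysis or ARDS unchanged.

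The cost is a phrase in each of two sentences and slightly more frequent pauses for DSMB review.

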8.5.1 Data Safety Monitoring Board (DSMB)

Safety oversight will be under the direction of a Data Safety Monitoring Board (DSMB) composed of [name] (Associate Chief of Staff for research at the VA NY Harbor Healthcare System and Associate Professor in the Division of Pulmonary, Critical Care, and Sleep Medicine) and [name] (Deputy Director of the Perlmutter Cancer Center and Professor of Oncology).

The members of the DSMB have appropriate medical and research expertise, and are not involved in this study. The DSMB will meet at least semiannually to assess safety and efficacy data on each research subject undergoing BCI. The primary responsibilities of the DSMB will be to periodically review and evaluate the accumulated study data for participant safety, study conduct and progress, and make recommendations concerning the continuation, modification, or termination of the trial. Pre-defined stopping rules are described in Section 8.4: Study Halting Rules. The outcome of each DSMB review and decision made (eg, continuing the study, continuing with modifications, suspending the study, or terminating the study) will be submitted to the IRB.

[name] will serve as a medical monitor who be responsible for overseeing participant safety. [name] has extensive expertise in both bronchoscopy and translational research. He will 1) review all AEs (including DLT and unanticipated events) on a regular basis throughout the trial; 2) be available to advise the investigators on trial-related medical questions or problems, and 3) evaluate cumulative participant safety data and make recommendations regarding the safe continuation of the study. He will identify/evaluate AE/SAEs, determine seriousness, severity, causality, and monitor and follow subjects to resolution. He will report the events and will notify the IRB. In the event of DLT, the IRB will be notified as soon as possible and within three days.

9 Clinical Monitoring

Clinical site monitoring is conducted to ensure that the rights and well-being of human subjects are protected, that the reported trial data are accurate, complete, and verifiable, and that the conduct of the trial is in compliance with the currently approved protocol/amendment(s), with GCP, and with applicable regulatory requirement(s).

- Monitoring for this study will be performed by an assigned medical monitor
- On-site monitoring will take place throughout the study, which will include a comprehensive review of all data and safety
- Details of clinical site monitoring are documented in a clinical monitoring plan. This describes in detail who will conduct the monitoring, at what frequency monitoring will be done, at what level of detail monitoring will be performed, and the distribution of monitoring reports.

10 Statistical Considerations

10.1 Statistical and Analytical Plans

All dose-limiting toxicities will be tabulated by type of DLT and dose level.

In addition to tabulating toxicities, we will record data on pre- and post-BCI peripheral blood biomarkers. For the continuous immunologic outcomes, we will calculate means by sampling time and perform exploratory graphical analyses, but with the small sample sizes and potentially irregular lengths of the series of observations it will not be possible to perform formal longitudinal analysis. We will apply non-parametric tests to evaluate changes in immunologic outcomes before and after BCI. Details are provided below.

